 - i. Subjects may withdraw voluntarily from study at any time upon their request.
 - ii. Subjects are inappropriately enrolled without fulfilling inclusion/exclusion criteria.
 - iii. Subjects develop spontaneous labour before IOL procedure is undertaken.
- b. Follow up process:
 - i. The withdrawn subjects will be managed according to local protocol under Department O&G, Sibu Hospital.
 - ii. The withdrawn subjects data will be destroyed as it will not be used for data analysis.
- c. The withdrawn subjects will be replaced with new subjects in order to meet the required sample size.

TREATMENT AND PROCEDURES

1. Treatment and medications that are permitted during the trial:
 - a. Amniotomy
 - b. Oxytocin augmentation when contractions are not optimised
 - c. Abdominal and vaginal examination to assess labour progress
 - d. Intrapartum continuous fetal heart rate monitoring
 - e. Fetal scalp sampling in the presence of non-reassuring fetal heart rate
 - f. Instrumental delivery or emergency Caesarean section if indicated

2. Both IOL methods of membrane sweeping and transcervical Foley catheter do not contain drug or medication. Thus, the risk of uterine rupture is similar to spontaneous labour in women with previous Caesarean delivery. If scar dehiscence is highly suspected during labour, standard management with recourse to emergency Caesarean section will be undertaken.

3. Treatment and medications that are not permitted during the trial:
 - a. Vaginal prostaglandin E2

ASSESSMENT OF EFFICACY

1. Primary outcome:
 - a. Overall induction to delivery interval.
2. Secondary outcomes:
 - a. Induction outcomes:
 - i. Improvement of modified Bishop score at interval of 24 hours and 48 hours after induction.
 - ii. Whether oxytocin augmentation is required.
 - b. Delivery outcomes:
 - i. Mode of delivery.
 - ii. Duration of oxytocin augmentation overall and in vaginal delivery group.
 - iii. Induction to vaginal delivery interval.

- iv. Amniotomy to vaginal delivery interval.
- v. Vaginal delivery rate within 24 hours of induction and between 24-48 hours of induction.
- c. Maternal outcomes:
 - vi. Uterine hyperstimulation (> 5 contractions per 10 minutes for at least 20 minutes or a contraction lasting at least 2 minutes with/without abnormal fetal heart rate).
 - vii. Uterine rupture.
 - viii. Post-partum haemorrhage (estimated blood loss \geq 500 ml).
 - ix. Maternal pyrexia (temperature >38.0 °C once, or 37.5 °C on two occasions 2 hours apart).

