 - i. No further membrane sweeping will be performed.
 - ii. Affected subject will be withdrawn from the study.
 - iii. No rescue medication is needed as condition is self-limiting.
 - iv. Closed monitoring of vital signs and oxygen saturation for 24 hours.
 - c. Cervical tear
 - i. Examination under anaesthesia will be performed immediately.
 - ii. Cervical repair will be performed.
 - iii. Subject will be followed up till 42 days post-delivery (completion of puerperal period).
 - d. Uterine rupture
 - i. Emergency laparotomy will be performed immediately.
 - ii. Depend on the severity of uterine rupture, uterine repair or hysterectomy may be warranted.

- iii. Subject will be followed up till 42 days post-delivery (completion of puerperal period).
 - e. Maternal sepsis
 - i. Blood culture and high vaginal swab for culture will be taken.
 - ii. Broad spectrum antibiotics will be started as rescue medication.
 - iii. Unstable subjects will be nursed in intensive care unit.
 - iv. Subject will be followed up till 42 days post-delivery (completion of puerperal period).
5. Compensation of adverse events
- a. In the event of a bodily injury or illness directly resulting from the membrane sweeping or transcervical Foley catheter insertion, the department will pay for reasonable and necessary treatment.
 - b. The department is not responsible for medical expenses due to pre-existing medical conditions, any underlying diseases, any ongoing treatment process, subjects' negligence or willful misconduct, the negligence or willful misconduct of the investigators or the study site or any third parties.

STATISTICS

1. All results will be analysed using the Statistical Package for Social Sciences for Windows (SPSS for Windows).
2. Normality of numerical data (Bishop score, induction to delivery interval, induction to vaginal delivery interval, amniotomy to vaginal delivery interval, duration of oxytocin augmentation, duration of hospitalisation, APGAR score at 5 minutes, cord pH, neonatal birth weight) will be assessed using Kolmogorov-Smirnov analysis. Independent T-test (data with normal distribution) or Mann-Whitney U test (if data not normally distributed) will be used to compare these outcomes between the group of membrane sweeping and group of transcervical Foley catheter.
3. Chi-square test will be used to compare:

- a. The requirement of oxytocin augmentation following induction between the group of membrane sweeping and group of transcervical Foley catheter.

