1. This study does not involve vulnerable subjects.

RESULTS (Dummy tables)**Table 1: Demographic characteristics**

Characteristics	Membrane sweeping	Transcervical Foley catheter	p-value
Age, years			
Parity			
Gestational age			
Ethnicity, n (%)			
Iban			
Melanau			
Bidayuh			
Malay			
Chinese			
Indian			
Others			
Foreigner			
Body mass index, kg/m ²			
Previous Caesarean section			
Tested scar			
Untested scar			
Indication of induction of labour			
Postdate			
Fetal growth restriction			
Hypertension			
Diabetes			
Others			

Table 2: Induction outcomes in two groups

Outcomes	Membrane sweeping	Transcervical Foley catheter	p-value
Bishop score at start of induction			
Bishop score after 24 hours of induction			
Bishop score after 48 hours of induction			
Change in Bishop score			
Oxytocin required			

Table 3: Delivery outcomes and maternal complications in two group

Outcomes	Membrane sweeping	Transcervical Foley catheter	p-value
Mode of delivery			
Vaginal			
Caesarean section			
Overall			
Induction to delivery interval			
Oxytocin augmentation duration			
Vaginal delivery			
Induction to delivery interval			
Amniotomy to delivery interval			
Oxytocin augmentation duration			

Within 24 hours of induction

Between 24-48 hours of induction

Indication for Caesarean section

Poor progress

Failed induction

Acute fetal distress

Suspected scar dehiscence

Others

Maternal complications

Uterine rupture

Uterine hyperstimulation

Post-partum haemorrhage

Maternal pyrexia

Duration of hospitalisation

Table 4: Neonatal outcomes in two groups

Outcomes	Membrane sweeping	Transcervical Foley catheter	p-value
APGAR score at 5 minutes			
Cord pH			
Birth weight			

[figure not shown]
REFERENCES

2. National Institute for Health and Clinical Excellence. *Inducing Labour*. NICE CG70. London: NICE; 2008.

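### Bishop score improvement has no single named analysis, and the recorded starting score is not used as a covariate, which gives up some precision and protection against chance imbalance

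*Combined protocol and SAP*

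**What the plan says.** Specific objective 2.a.i and Assessment of Efficacy 2.a.i both concern improvement in cervical score; the latter reads "Improvement of modified Bishop score at interval of 24 hours and 48 hours after induction".

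Statistics, item 2, opens its list of variables with "Normality of numerical data (Bishop score, induction to delivery interval" and then states: "Independent T-test (data with normal distribution) or Mann-Whitney U test (if data not normally distributed) will be used to compare these outcomes". The Bishop score appears there without a time point, without being defined as a change, and without a covariate. No regression or other adjusted analysis appears anywhere in the protocol.

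Dummy Table 2 has one p-value column and four Bishop rows: "Bishop score at start of induction", "Bishop score after 24 hours of induction", "Bishop score after 48 hours of induction" and "Change in Bishop score". The last does not say whether it runs to 24 h or to 48 h.

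The starting score is collected for each woman (Appendix 3, Section B), and entry requires a score of 6 or less (Selection and Withdrawal, item 2). Statistics, item 4, sets 0.05 as the threshold for every test.

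**The concern.** The objective is improvement, but nothing says which row of Table 2 answers it. A raw 24 h score does not itself measure improvement. The change row does, but it could refer to either time point. If the arms differ by chance in starting ripeness, the two forms give different estimates, and in an open-label trial the choice between them should be made before the data are seen.

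Neither form makes good use of the starting score. The raw comparison ignores it. The change score subtracts it with a fixed coefficient of 1, whatever the data show about how strongly it predicts the later score. A model with the starting score as a covariate estimates that coefficient. The p-value beside the starting score adds nothing: after randomisation any difference there is due to chance, and testing it does not correct it.

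At stake are the clarity and precision of one secondary outcome.

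**Working it through.** **Nothing to reproduce.** The documents give no SD, effect size, power or sample size for the Bishop score. The sample size formula is for the induction to delivery interval, and no final number is stated. The only count given is the first stage of 24 women, 12 per arm.

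**Assumed inputs.** rho is the correlation between starting and 24 h score, varied from 0.2 to 0.7. r is the starting SD divided by the 24 h SD, varied from 0.5 to 1. Figure 1 of the protocol gives a maximum score of 3 + 3 + 3 + 2 + 1 = 12, while entry is capped at 6. The cap narrows the starting spread, so r below 1 is plausible, and it may also lower rho.

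**Large-sample variance of the arm difference, relative to the raw 24 h comparison:**
- Raw: 1
- Change: 1 + r² − 2·rho·r
- ANCOVA: 1 − rho²

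ANCOVA is lower than raw by rho² and lower than change by (r − rho)², so in large samples it is never worse than either. Change beats raw only when rho exceeds r/2, so neither planned form is always the better one.

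**Extra women needed for the same precision as ANCOVA (variance ratio minus 1):**

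| rho | Raw | Change, r = 1 | Change, r = 0.75 | Change, r = 0.5 |
|---|---|---|---|---|
| 0.2 | 4% | 67% | 32% | 9% |
| 0.3 | 10% | 54% | 22% | 4% |
| 0.5 | 33% | 33% | 8% | 0% |
| 0.7 | 96% | 18% | 0% | 8% |

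Example, rho = 0.3 and r = 0.75: change = 1 + 0.5625 − 0.45 = 1.1125; ANCOVA = 1 − 0.09 = 0.91; ratio = 1.22.

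**Small samples.** Estimating the slope costs a factor of about (N − 3)/(N − 4). At N = 24 this is 21/20 = 1.05, so ANCOVA beats raw only if 1.05 × (1 − rho²) < 1, that is, rho above about 0.22. At N = 100 the break-even is about 0.10.

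**Chance imbalance.** If starting means differ by D, the raw and change estimates differ by exactly D (same women in both). With 12 per arm, D has a standard error of √(2/12) = 0.41 starting SDs.

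**How often the two forms disagree.** A simulation used 20,000 replicates with normal scores, rho 0.2 to 0.7, 12 or 50 women per arm, and an effect giving the raw test nominal 80% power. The raw and change tests at one time point fell on opposite sides of 0.05 in about 21% to 30% of trials at r = 1, and 11% to 19% at r = 0.5. With no effect, at least one of the two was significant in about 8.5% to 9.6% of trials (r = 1) or 7.1% to 7.8% (r = 0.5), against a nominal 5%.

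**The 48 h score.** Under Trial Design, Study procedure, item m, women with a favourable cervix at 24 h proceed to amniotomy. The 48 h scores therefore come from a group selected after randomisation, and adjustment for starting score does not repair that. Vaginal delivery within 24 h is itself a listed outcome, so some 24 h scores may be missing too.

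**The case against.** The strongest reply is that the planned tests are valid and that this is a labelling gap on a secondary outcome. Much of that stands:

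- A reader might infer that the change score is biased by regression to the mean. It is not: both arms share the same expected regression, so the comparison is unbiased over randomisation. Change over-corrects a chance imbalance only when the slope rho/r is below 1.
- A reader might take a one-third to one-half loss for the change score as established. The 33% and 54% figures need equal SDs at start and 24 h. The documents do not support that assumption, and the entry cap makes a smaller starting SD plausible; at r = 0.5 the same two values of rho give 0% and 4%.
- Four rows are not four rival answers. The starting score is not an answer, and 24 h and 48 h are both named in advance. Only raw and change compete.
- The text leans towards change. The outcome is improvement, and the description of Section B under Study instruments refers to serial changes. The variable list in Statistics may simply be shorthand.

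The reply does not remove two facts: no row is named as the analysis of objective 2.a.i, with the change row undated, and a covariate already collected goes unused.

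**Conclusion.** The point holds as a modest, inexpensive improvement. The plan should name one analysis for objective 2.a.i and adjust it for starting score. The case for naming one does not depend on the size of the gain.

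That size cannot be derived from the documents. It runs from about 4% to 96% more women for the raw score and 0% to 67% for the change score, over assumed rho of 0.2 to 0.7 and r of 0.5 to 1. In the first 24 women the gain over the raw score could be nil.

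A reader might infer that the planned results would be invalid, or that the trial is undersized because of this. The documents support neither: randomisation protects both comparisons, and the sample size is to be based on the induction to delivery interval.

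**What to change.** In Statistics, name the analysis for objective 2.a.i: the 24 h modified Bishop score regressed on arm and starting score, reported as an adjusted mean difference with 95% CI. Add a rank-based ANCOVA as a check if residuals are clearly non-normal.

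In Table 2:
- Show the starting score without a p-value.
- Replace the undated change row with two descriptive rows, '24 h minus start' and '48 h minus start'.
- Add one row for the adjusted 24 h difference, and let it alone carry the inference.
- Keep the 48 h score as a reported outcome, labelled descriptive, with the reason: women favourable at 24 h go on to amniotomy.

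State how women without a 24 h or 48 h score are handled.

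The cost is a few sentences, a relabelled table and slightly more analysis work, with no new data. The downside is a linear model on a bounded score, which the rank-based check addresses in part.

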With the global rise in Caesarean section, more and more women embark on pregnancy with previous Caesarean scar (3). It is estimated that one in every four term pregnancies requires IOL (4). With IOL in previous Caesarean section, the risk of uterine scar rupture with subsequent catastrophic maternal and neonatal outcomes is the greatest concern (5). Previous influential study (6) highlighted that IOL with prostaglandin conferred the greatest risk of uterine rupture (2.45%) in women with one previous Caesarean delivery. On the other hand, the risks of uterine rupture were lower and comparable among women whose labour induced without the use prostaglandin (0.77%) and women with spontaneous labour (0.52%). Among the various IOL methods, prostaglandin is more likely associated with shorter interval to achieve vaginal delivery and avoidance of oxytocin augmentation (7). Nevertheless, mechanical methods have lower risk of uterine hyperstimulation (7, 8) but have more risk of infection (7). As a result, obstetricians are facing dilemma on deciding the safe and effective method of IOL in women with previous Caesarean delivery.

In Sibug Hospital, membrane sweeping is routinely offered to women with previous Caesarean delivery who require IOL. This technique involves the examining finger passing through the cervix to rotate against the wall of the uterus, to separate the chorionic membrane from the decidua, or to massage around the cervix if the os is closed (1, 2). However, membrane sweeping may not exert its cervical ripening effect immediately and the delivery may be delayed by up to 8 days (9). This may render a proportion of women to resort to repeated Caesarean section for failed induction. The vaginal birth rates following membrane sweeping in women with unscarred uterus are ranging between 78%-90% (10-12). Among women with previous Caesarean delivery undergoing IOL with membrane sweeping, the reported vaginal birth rates were conflicting. A randomised controlled trial by Hamdan et al. showed vaginal

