- j. In Group 2, transcervical Foley catheter No. 18 F will be inserted under aseptic technique into the endocervical canal surpassed beyond the internal os. The balloon will be inflated with 60 ml of sterile water and the catheter is plastered to patient's thigh with gentle traction. The catheter will be checked for its position and the traction at 6 hours interval. If it were expelled spontaneously, it would not be re-inserted. Otherwise, the catheter will be removed after 24 hours.
- k. Post-induction CTG will be performed at 1 hour after the first membrane sweeping in Group 1 and after transcervical Foley catheter insertion in Group 2.
- l. The uterine contractions, maternal temperature and fetal heart rate (via handheld Doppler device) will be monitored every 4 hours.
- m. After 24 hours, improvement of modified Bishop score will be assessed.
 - i. If the cervix is favourable for amniotomy, amniotomy will be performed followed by augmentation with intravenous oxytocin.

- ii. If the cervix is still unfavourable and amniotomy is impossible, membrane sweeping will be continued for one more day in Group 1 whereas conservative management will be undertaken for one day in Group 2. Suitability for amniotomy will be reassessed on the next day.
 - n. After amniotomy, subsequent intrapartum management will be based on the hospital protocol.
 - o. Oxytocin augmentation will be started when desired contractions are not achieved at 2 hours after amniotomy or labour progress falls below the action line of partogram.
 - p. Our oxytocin infusion regime begins with 2 mU/min. An increment in dosage is made every 30 minutes until desired contractions of 3-4 in 10 minutes lasting 45-60 seconds. The maximum oxytocin dose is 16 mU/min.
 - q. Continuous CTG monitoring will be undertaken throughout the labour process.
 - r. Oxytocin augmentation will not be started or will be withheld when there is non-reassuring fetal heart rate.
 - s. If amniotomy is still impossible after 2 days of IOL, the ward Obstetrician will discuss with women regarding option of Caesarean section.
6. Criteria for suspending or terminating the study:

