b) After 48 hours of induction

(only applicable to Foley group)

Achieved favourable Bishop (≥ 8) score: *(please tick)*

Yes

No

(if yes, proceed to sub-question;

if no, proceed to next question)

a) Interval to achieve favourable Bishop score

_____ (hours)

Achieved cervix allowing amniotomy: *(please tick)*

Yes

No

(if yes, proceed to sub-question;

if no, proceed to next section)

a) Bishop score at that time

b) Os dilatation at that time

_____ (cm)

c) Cervical length at that time

_____ (cm)

SECTION C: DELIVERY OUTCOMES

Oxytocin required during delivery (*please tick*) Yes No

Mode of delivery: (*please tick*)

- Vaginally Within 24 / 24-48 / > 48 hours of induction (*please circle*)
- Instrumentation Vacuum / forceps (*please circle*)
Indication: _____
- Caesarean section Indication: _____

Durations (regardless of final mode of delivery):

- a) Induction to delivery _____ (hours)
- b) Oxytocin augmentation _____ (minutes)

Durations (only for vaginal delivery including instrumental delivery):

- a) Induction to vaginal delivery _____ (hours)
- b) Amniotomy to vaginal delivery _____ (hours)
- c) Oxytocin augmentation _____ (minutes)

Estimated blood loss (EBL): ml

If EBL > 500ml, please mention cause: (*please tick*)

- a) Uterine atony
- b) Perineal trauma
- c) Retained placenta
- d) Coagulopathy
- e) Others *Please specify:*

Maternal complications: (*please tick*)

- a) Uterine rupture Yes No
- b) Uterine hyperstimulation Yes No
- c) Post-partum haemorrhage Yes No
- d) Maternal pyrexia Yes No

Neonatal outcomes:

- a) APGAR score at 5 minutes _____ To: NICU / SCN / mother (*please circle*)
- b) Cord pH _____
- c) Birth weight _____

SECTION D: MATERNAL SATISFACTION

If you had to repeat it all over again, would you take part in the study? (*please tick*)

Yes

No

If no, please provide reason(s). _____

Notes:

Uterine hyperstimulation : > 5 contractions per 10 minutes for at least 20 minutes or a contraction lasting at least 2 minutes with/without abnormal fetal heart rate

Post-partum haemorrhage : Estimated blood loss \geq 500 ml

Maternal pyrexia : Temperature >38.0 °C once, or 37.5 °C on two occasions 2 hours apart

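### A Caesarean for failed induction before amniotomy falls by default into the same 'No' as a labour that needed no oxytocin, so unequal failure rates can create a spurious difference in the oxytocin outcome

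*Combined protocol and SAP*

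**What the plan says.** Assessment of Efficacy, 2.a.ii, lists "Whether oxytocin augmentation is required" among the induction outcomes. Statistics 3.a applies a chi-square test to "The requirement of oxytocin augmentation following induction between the group of membrane sweeping and group of transcervical Foley catheter". Neither place states a denominator or restricts the comparison to women who reach amniotomy or labour. Dummy Table 2 has one row for the outcome. Section C of the data collection form (Appendix 3) has one item, "Oxytocin required during delivery", to be ticked Yes or No.

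Trial Design, section 5, sets out how a woman comes to receive oxytocin:

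- Step 5.m.i: "If the cervix is favourable for amniotomy, amniotomy will be performed followed by augmentation with intravenous oxytocin".
- Step 5.o: "Oxytocin augmentation will be started when desired contractions are not achieved at 2 hours after amniotomy or labour progress falls below the action line".
- Step 5.s: "If amniotomy is still impossible after 2 days of IOL, the ward Obstetrician will discuss with women regarding option of Caesarean section". No oxytocin step appears on this path.

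Failed induction is not among the withdrawal criteria, so these women stay in the analysis. The introduction accepts that slow ripening after sweeping may lead some women to a repeat Caesarean for failed induction. It also names "avoidance of oxytocin augmentation" when describing what prostaglandin achieves relative to other methods.

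**The concern.** The 'No' answer pools two opposite results. One is a woman who laboured without needing oxytocin. The other is a woman whose cervix never allowed amniotomy and who had a Caesarean before oxytocin arose. A lower oxytocin rate may therefore mean that induction worked better or that it failed more often, and the planned test cannot tell these apart.

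The less effective method could be reported as significantly reducing the need for oxytocin when use among women who reached amniotomy or labour was the same in both arms, or even higher with that method. Unequal failure is plausible: relative effectiveness is the trial's question, and the arms are managed differently on the second day (sweeping continues in Group 1, conservative management in Group 2).

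**Working it through.** **Plan's own figure.** There is none to reproduce. The documents give no rate for oxytocin use or failed induction. They fix only the 24 women (12 per group) of the interim stage and defer the final sample size. All rates and group sizes below are assumptions.

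**Model.** Let f be the share of an arm having a Caesarean for failed induction before amniotomy, and q the share given oxytocin among the rest. With failures recorded as 'No':

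- observed oxytocin rate = q × (1 − f)
- with equal q in both arms, spurious gap = q × (difference in f)

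**Chance of a significant result.** This uses the uncorrected chi-square at two-sided 0.05 (the plan does not state sidedness) with 75 women per arm, summing exact binomial probabilities. The true difference in q is zero in every row.

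| f (arm A v B) | q | Observed rate A v B | Gap (points) | p<0.05 |
|---|---|---|---|---|
| 10% v 10% | 60% | 54% v 54% | 0 | about 5% to 6% |
| 10% v 10% | 90% | 81% v 81% | 0 | about 5% |
| 15% v 10% | 60% | 51% v 54% | 3 | 7% |
| 15% v 10% | 90% | 76.5% v 81% | 4.5 | 10% |
| 20% v 10% | 60% | 48% v 54% | 6 | 12% |
| 20% v 10% | 90% | 72% v 81% | 9 | 25% |
| 30% v 10% | 60% | 42% v 54% | 12 | 33% |
| 30% v 10% | 90% | 63% v 81% | 18 | 70% |

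Hand check of the last row by normal approximation:

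- Pooled rate = (0.63 + 0.81)/2 = 0.72.
- Null standard error = √(2 × 0.72 × 0.28/75) = 0.0733, so the critical gap is 1.96 × 0.0733 = 0.1437.
- Standard error under the alternative = √((0.63 × 0.37 + 0.81 × 0.19)/75) = 0.0718.
- (0.18 − 0.1437)/0.0718 = 0.51, giving a probability of about 69%.

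**Other group sizes.** At q = 80% and failure of 30% v 10% (56% v 72%), p<0.05 occurs in about 38% of trials with 50 per arm and 66% with 100 per arm.

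**Reversal.** Suppose the arm with 30% failure uses more oxytocin among women who reach amniotomy or labour, 70% against 60%. Observed rates are 0.70 × 0.70 = 49% and 0.60 × 0.90 = 54%, so that arm still shows the lower overall rate.

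**If oxytocin always follows amniotomy.** Step 5.m.i can be read this way. Then q is close to 100%, and at 30% v 10% failure the outcome becomes 70% v 90%. It would measure little beyond whether amniotomy was reached. The problem survives either reading of 5.m.i and 5.o.

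**Three categories.** At q = 80% and failure of 30% v 10%:

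- oxytocin given: 56% v 72%
- no oxytocin, other: 0.20 × 0.70 = 14% v 0.20 × 0.90 = 18%
- failed induction, no oxytocin: 30% v 10%

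The reader now sees that the lower first figure comes from the third line.

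**The case against.** Several points on the other side stand.

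- **The coding is inferred.** A reader might take the plan to contain a rule that a failed induction counts as oxytocin not required. It does not. The 'No' follows from a two-option item and an unrestricted comparison. Staff could leave the item blank, or the analyst could exclude the woman, but those choices are also unspecified and would be made in an unblinded trial.
- **The pathway is not airtight.** Step 5.s describes a discussion of Caesarean and does not say that every such woman has one. The list of permitted treatments allows oxytocin for suboptimal contractions without mentioning amniotomy. This may reduce the number affected, but it does not separate the two kinds of 'No'.
- **The direction of bias is unknown.** A reader might infer that the outcome will favour sweeping. The documents give no failure rates and do not establish which arm will fail more often. With equal failure there is no bias.
- **The outcome is worded neutrally.** The remark about avoiding oxytocin concerns prostaglandin and does not declare a favourable direction for this trial. Oxytocin exposure among all women analysed is a legitimate quantity to report. The difficulty lies in reading a lower figure as better induction.
- **The failures are partly visible.** Table 3 shows mode of delivery and failed induction as a Caesarean indication by group, so an imbalance could be noticed. The p-value in Table 2 still ignores it.

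It is also tempting to test vaginal delivery without oxytocin instead. That is a different outcome: it falls with every Caesarean, whatever the indication, and overlaps with mode of delivery, which is already tested.

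**Conclusion.** The concern holds for this secondary outcome. Followed as written, with failures recorded 'No' by default, the plan can yield a significant difference in oxytocin requirement that reflects only a difference in failed induction.

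Its size depends on the assumed failure gap. With q of 60% to 90% and 75 women per arm, the gap is 6 to 9 points at 20% v 10% failure and 12 to 18 points at 30% v 10%; p<0.05 occurs in about 12% to 25% and 33% to 70% of trials respectively. The upper figures need a threefold difference in failure and should not be read as expected values.

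A reader might infer that the trial's main conclusion is at risk. The documents do not support that: the primary outcome, overall induction to delivery interval, and its sample size calculation do not use the oxytocin item.

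**What to change.** In outcome 2.a.ii, Statistics 3.a and Table 2, report and compare three exclusive categories in all analysed women:

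1. oxytocin given;
2. no oxytocin, other than category 3;
3. no oxytocin, and Caesarean for failed induction with the form's 'cervix allowing amniotomy' item marked No.

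The form already holds the fields: oxytocin, cervix allowing amniotomy, mode of delivery and Caesarean indication. State the denominator. Add that a lower 'oxytocin required' rate will not be interpreted as a benefit unless category 3 is no higher in that arm. Vaginal delivery without oxytocin could at most be an additional descriptive row.

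Steps 5.m.i and 5.o differ on when oxytocin is started and must be reconciled, because the meaning of the outcome depends on them.

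The cost is wording in three places and no new data. There are two small downsides. A three-level comparison is less simple than one percentage. Category 3 relies on the recorded Caesarean indication, because the form has no field for labour onset.
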